Evaluation of intervention impact. Data will be analyzed with an intent-to-treat approach.179 Randomization at the social network level will likely balance cluster-level baseline characteristics; however, as randomization may not precisely balance these, and there may be differences in social network member characteristics after network randomization, inverse probability weighting using propensity scores will be explored to balance baseline characteristics (both network and individual) between arms₁₈₀ using best practices.₁₈₁ Balance on propensity scores between intervention groups will be assessed using standardized differences.182 Propensity scores have been used in cluster RCTs.183 We will evaluate the intervention impact by comparing rates of past 6-month COVID-19 testing and vaccination completion (defined as complete dosage of approved vaccination: e.g., 2 Pfizer or Moderna doses or 1 Johnson & Johnson dose) between intervention and delayed-intervention group social network members at immediate post intervention (6 months after the intervention group *Navegantes* are trained), adjusting for baseline rates. This ANCOVA approach has the advantage of being unaffected by baseline differences; if baseline rates, by chance, were different, the intervention effect would be overestimated by looking at change scores and underestimated by a follow-up score analysis. The ANCOVA approach gives the same answer regardless of baseline imbalance. Additionally, the approach generally has greater statistical power to detect an intervention effect than the other methods. 184 Statistical analysis will be performed using generalized linear mixed modeling 185 for binary outcomes (sometimes termed randomeffects logistic regression). These models can assume a logit link for binary data (i.e., tested or vaccinated in past 6 months: yes/no) and allow for accounting for the within-group association of outcomes. If participants have repeated COVID-19 testing performed then an additional random effect for multiple testing will be considered, where appropriate. The generalized linear mixed model is an extension of general linear models that allows for non-independence of observations (e.g., within social networks).

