The hypothesis that intervention and delayed-intervention groups differ in their prevalence, p, of COVID-19 testing or vaccination will be tested with the mixed-effects logistic model: Logit $(p_{ij}l) = \beta_0 + \beta_1 Y_{ijo} + \beta_2 INTVN + v_i$, where $p_{ij}l$ is the probability of testing or vaccination at immediate post-intervention for participant i in social network j, Y_{ij0} is 1 if participant i in social network j reports testing or vaccination at baseline and 0 otherwise, and, INTVN =1 for the intervention group and 0 for the delayed-intervention group. The random effect v_j is the random effect for participants in social network j. The variance component for this random effect addresses the within-social network correlation. Under this model, β_2

corresponds to the difference in prevalence of testing or vaccination at immediate post-intervention between the intervention and delayed-intervention groups on the logit scale. This random-effects logistic regression model will be fit using adaptive Gaussian quadrature in SAS PROC GLIMMIX.186

This regression approach will allow us to produce estimates of prevalence and prevalence change additionally *adjusting for individual and cluster-level covariates*, which will be compared to unadjusted estimates. Individual-level covariates may include age, country of origin, employment status, and education level. Because there are only a small number of clusters (social networks), the literature advises that the number of cluster-level covariates should be limited to one or two key variables. 187, 188 To assess the importance of covariates, we will use a backwards elimination model building approach, with primary consideration on assessment of confounding on the intervention-group difference. If confounding is present (defined to be greater than a 10% change in the regression estimate of the intervention-group effect), the confounder will be retained in the multivariable model. If many confounders are retained, alternative/sensitivity analyses will be conducted using propensity score weighting. All analyses will be 2-sided. 189 Note: While a better understanding of the relationships between members of social networks can be interesting, social network analysis is beyond the scope of this proposal based on our hypotheses and analysis plans.

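### The additional covariate-adjusted estimate is built with a 10% change-in-estimate rule whose bar moves with the estimated effect; a short covariate list fixed in advance is a cheap improvement

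*Combined protocol and SAP*

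**What the plan says.** In the Analytical Plan for Aim 2 (Evaluation of intervention impact), the difference between arms "will be tested with the mixed-effects logistic model". That equation holds the outcome at baseline, the arm indicator and a random effect for social network, and nothing else. The plan then adds covariate-adjusted estimates, "which will be compared to unadjusted estimates". For these it gives:

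- **Candidates.** "Individual-level covariates may include age, country of origin, employment status, and education level", so the list is open. On network-level variables it notes that "the number of cluster-level covariates should be limited to one or two key variables", but names none.
- **Method.** "we will use a backwards elimination model building approach, with primary consideration on assessment of confounding on the intervention-group difference".
- **Threshold.** Confounding is "defined to be greater than a 10% change in the regression estimate of the intervention-group effect", and a covariate that meets it stays in the model.
- **Fallback.** "If many confounders are retained, alternative/sensitivity analyses will be conducted using propensity score weighting". How many counts as many is not stated. Earlier in the same section, and independently of this rule, "inverse probability weighting using propensity scores will be explored to balance baseline characteristics".

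Baseline data are collected before networks are randomized (Objectives, Aim 2; Design, Aim 2). The plan labels neither model primary or secondary. I read the adjusted estimate as supporting because the hypothesis is tied to the equation without selected covariates. The plan also does not say whether the 10% is measured against the full model or the current one.

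**The concern.** Among all those randomized, baseline imbalance between arms is due to chance. A screen for it should respond to how unbalanced and how prognostic a covariate is. This rule responds to both, but also to something irrelevant: the size of the estimated intervention effect. The same covariate with the same imbalance is called a confounder if the intervention looks weak and is dropped if it looks strong.

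At stake is an adjusted odds ratio whose covariates are settled by the outcome data, so it cannot be specified beforehand, and whose standard error ignores the selection. Network-level variables are the most exposed, because with 10 networks per arm their chance imbalance is large.

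**Working it through.** **The plan's own figure.** The only figure available is the sample size: 20 networks x 8 members = 160, which agrees. The Sample Size section gives no rates, effect, intraclass correlation (ICC), alpha or power, and the plan states no operating characteristic for the selection rule. The rest therefore rests on assumptions, which are stated.

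**Step 1: the bar.** Bar = 0.10 x |estimated log odds ratio|. In simulation of this design the standard error of that estimate is near 0.40.

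| Estimated log OR | Bar | Bar / 0.40 |
|---|---|---|
| 0.1 | 0.01 | 0.025 SE |
| 0.5 | 0.05 | 0.125 SE |
| 1.0 | 0.10 | 0.25 SE |

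The bar is a small fraction of a standard error throughout and goes to zero with the effect. This needs no assumption beyond the approximate standard error.

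**Step 2: how often unrelated covariates are kept.** Assumed: 10 v 10 networks of 8, control rate 40%, baseline-outcome OR 2 with prevalence 40%, ICC 0.05, one binary 50/50 covariate with within-network correlation 0.10 (or one network-level covariate present in 10 of 20 networks), 6,000 trials per cell, and the 10% rule as sole criterion.

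| True intervention OR | 1 | 1.5 | 2 | 3 |
|---|---|---|---|---|
| Unrelated, individual-level | 37% | 24% | 13% | 4% |
| Unrelated, network-level | 51% | 43% | 32% | 20% |
| Covariate with OR 3 | 77% | 69% | 56% | 43% |

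Over control rates of 20-60% and ICC 0.01-0.10, the first row ranges over 33-39%, 13-18% and 4-7% at true OR 1, 2 and 3. In the most unbalanced third of trials, an unrelated covariate is kept in 60%, 27% and 11% at true OR 1, 2 and 3, so retention falls as the effect rises even where imbalance is high.

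A separate simulation used five unrelated candidates (four individual-level, one network-level), full-model reference and 2,000 trials per setting. It kept at least one in 82%, 63% and 38% of trials at log OR 0, 0.5 and 1.0. Each individual-level candidate was kept in about 34%, 20% and 7%, and the network-level one in 57%, 42% and 24%.

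**Step 3: what selection does to the adjusted estimate.** Retention alone is not harm, since a fixed list keeps every listed covariate. The relevant comparison is selection against a fixed list.

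| Candidates | Test | Selected | Fixed list |
|---|---|---|---|
| 4 individual + 2 network | z | 7.6% | 5.8-6.0% (short list) |
| 4 individual + 2 network | t, 18 df | 5.4% | 4.2-4.4% (short list) |
| 4 individual + 1 network | t, 18 df | 5.7-5.9% | 4.6% (two covariates); 5.1-5.2% (all five) |
| 4 individual only | t, 18 df | 4.2-4.5% | 4.1-4.2% (all four) |

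These are type I errors at nominal 5% (the plan states no alpha). With six candidates the gap is 7.6 - 6.0 = 1.6 to 7.6 - 5.8 = 1.8 points with z, and 5.4 - 4.4 = 1.0 to 5.4 - 4.2 = 1.2 with t. The SD differs by 3-7%, the short list's standard error is closer to the true SD, and power is equal.

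In the five-candidate runs the SD ratios are 0.421 / 0.405 = 1.04 and 0.445 / 0.426 = 1.04, in line with that range; the Monte Carlo standard error of those type I errors is about 0.5 points. With the four individual-level candidates alone there is no gain: power is equal, and fixing all four makes the SD slightly larger.

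**The case against.** The strongest reply is that the governing test is untouched. The hypothesis model is written out, the adjusted estimate is set beside the unadjusted one, and selection costs no power. That stands, and it limits the point to a supporting estimate.

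Second, a fixed list keeps an unrelated covariate every time, so high retention is no argument for fixing the list. That also stands. The case rests on Step 3, and it favours a short list, not a long one.

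Third, the comparison can flatter the remedy. In one five-candidate scenario the two fixed covariates were exactly the prognostic ones. That is fair, but where all five were unrelated to the outcome the gap was similar (5.7% v 4.6%).

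Fourth, the simulations are narrower than the plan. The plan calls confounding the primary consideration, not the only one. Dropout was not simulated, and loss over six months could create imbalance that is not due to chance. The percentages are therefore indicative; the scaling of the bar is not affected.

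Fifth, an open list fits measures that are still draft in Table 2. That explains the wording now, but does not prevent fixing the list before outcome data are seen.

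Several stronger readings are tempting and not supported:

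- **That the trial's main result is at risk.** The tested equation contains no selected covariate.
- **That the rule ignores imbalance.** It tracks both imbalance and prognostic strength, though not only those.
- **That propensity weighting hangs on this rule.** The plan explores weighting separately.
- **That unrelated variables will be published as confounders.** The plan does not say this.
- **That non-collapsibility of the odds ratio, disagreement between the two models, or the chance to quote the better of the two argues for a fixed list.** A fixed adjusted model leaves all three essentially as they are.

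**Conclusion.** The concern holds as a modest one. The retention bar scales with the estimated effect, so unrelated covariates, above all network-level ones, often enter the adjusted model, most often when the effect is small.

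The consequence is confined to the adjusted estimate and depends on network-level variables being among the candidates. With two of them, type I error is about 7.6% (z) or 5.4% (t) under selection, against about 6% or 4.3% for a short fixed list, with an SD 3-7% larger and a standard error somewhat too small. With none, there is no material difference. These sizes rest on an assumed control rate of 40%, ICC of 0.05 and the 10% rule as sole criterion, none of which the documents settle. This is a worthwhile improvement, not a defect in the hypothesis test.

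**What to change.** Replace the elimination step with one adjusted model whose covariates are fixed before outcome data are seen: two or three from age, education, employment and country of origin, plus at most one named network-level variable. Keep all of them whatever the data show. State that this model supports the fixed hypothesis-test equation. If the 10% rule is kept at all, label its result exploratory. Since the number of covariates retained would no longer trigger the weighted sensitivity analysis, say directly whether that analysis will be run.

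The cost is SAP wording; matching variables are already among the draft demographic measures in Table 2. The downside is a small loss of precision if a listed covariate is not prognostic. In the five-candidate simulation with all covariates unrelated to the outcome, fixing two raised the SD from 0.395 to 0.405 (0.405 / 0.395 = 1.025, or 2.5%), while fixing all five raised it to 0.427 (0.427 / 0.395 = 1.081, or 8%). That is the reason to keep the list short.
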